### **Clinical Remission on Medications:**

- Inactive disease as defined above for 6 months (24 weeks) continuously while on medications.

Clinical inactive disease and clinical remission status will be based on the investigator’s assessment of the above components.

Note that when calculating clinical remission, only inactive disease in this study will be included in the 24 weeks count.

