6.1.2. Subjects with Combined End of Qualifying/Index Study Visit/LTE Screening/Baseline Visit

Subjects who complete their combined Screening/Baseline Visit on the same day as EOS in the qualifying/index tofacitinib study must also complete the following procedures:

- Informed consent/Assent obtained.
- AE assessment.
- Risk factor check for venous thromboembolism (see [Section 7.2.10](#)).
- Confirm highly effective contraception is being used.
- Dispense study medication and provide dosing instructions/schedule next visit.

6.1.3. Subjects with Separate End of Qualifying/Index Study Visit and Combined LTE Screening/Baseline Visit

Subjects who complete their combined Screening/Baseline Visit within 14 days of EOS in the qualifying/index tofacitinib study but not on the same day as EOS must complete the following procedures at the combined Screening/Baseline Visit:

- Informed consent/Assent obtained.
- AE assessment.

- Risk factor check for venous thromboembolism (see [Section 7.2.10](#)).
- Concomitant medications (ongoing or started since last visit in qualifying/index study).
- Vital signs: temperature (oral, tympanic or temporal preferred), BP and PR. For subjects with sJIA: temperature must be measured orally using a digital thermometer, with the exception of very young children or others who cannot tolerate an oral thermometer. In these cases temperature may be measured rectally using a digital thermometer. The definition of fever with a rectal thermometer is one degree Fahrenheit higher. (Example >101.4°F/38.6°C rectally compared to >100.4°F/38°C orally).
- Targeted physical exam, including weight and height.
(**Applicable to subjects enrolled from Study A3921165:** a skin examination for chicken pox or shingles must be performed).
- Physician global evaluation of disease activity.
- Joint assessment of active arthritis (swelling, pain/tenderness), and limitation of motion.
- Duration of morning stiffness.
- Safety laboratory testing (chemistry, hematology, urinalysis), including urine pregnancy testing (β -hCG) for females of child-bearing potential.
- Confirm highly effective contraception is being used.
- CRP.
- ESR determination (Westergren Method).
- Dispense study medication and provide dosing instructions/schedule next visit.

sJIA subjects ONLY:

- Assessment of JIA-associated fever: Fever is defined as temperature >38°C/100.4°F). Refer to [Section 7.1.10.1](#) for details.

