7.1.5. Inflammatory Markers

In this study, testing for both Erythrocyte Sedimentation Rate (ESR) and C-Reactive Protein (CRP) will be performed in all subjects at each study visit except Screening/Baseline Visit for subjects who roll over on the same day of EOS from their Index Studies (see [Schedule Of Activities](#)).

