6. Intra-articular steroid (eg, triamcinolone (KENALOG[®], Aristospan[®])) should be administered to no more than four joints in any given 6 month period and individual joints should not be injected any more frequently than once in a 6-month period. Injected joints will be considered as not assessed during the remainder of the study. Intra-articular injections should be avoided during the 6 weeks prior to a study visit.

A UNIFORM TAPERING OF A MEDICATION OR TITRATING UP ON A DOSAGE OF MEDICATION TOWARD A SPECIFIC PRE-DETERMINED GOAL DOSAGE (INCLUDING DISCONTINUATION) WILL BE CONSIDERED A SINGLE CHANGE IF ACCOMPLISHED WITHIN 1 MONTH.

Appendix 4. Permitted Adjustments (Tapering) of JIA Medications for Subjects with Inactive Disease for at Least 24 Weeks

Subjects who have inactive disease for at least 24 consecutive weeks may begin to taper off of concomitant JIA therapies and tofacitinib. Tapering of therapies is to be completed in the following order: oral corticosteroids, MTX/leflunomide, tofacitinib.

- For subjects who are not taking concomitant oral corticosteroids, tapering will start with MTX/leflunomide, followed by tofacitinib.
- For subjects who are not taking concomitant MTX/leflunomide, tapering will start with oral corticosteroids, followed by tofacitinib.
- For subjects not taking concomitant oral corticosteroids or MTX/leflunomide, tapering will start with tofacitinib.

The rate at which each drug is tapered is described below.

Oral Corticosteroids: The dose of oral corticosteroids may be reduced or discontinued for subjects who have inactive disease for at least 24 consecutive weeks (time in parent study and A3921145 inclusive). The dose can be reduced by 0.1mg/kg each week. Once the dose of corticosteroids is at 5 mg/day then an absolute decrease by 1 mg/day each week can be implemented.

Methotrexate/leflunomide: The dose of MTX/leflunomide may be decreased or discontinued for subjects who continue to have inactive disease for at least 24 consecutive weeks after receiving the last dose of oral corticosteroids. MTX/leflunomide may be discontinued with or without tapering based on local practice; it is acceptable to stop the drug abruptly or by tapering the dose.

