#### **3.2. Secondary Endpoints**

The following efficacy parameters will be assessed:

- Change from baseline in physician global evaluation of disease activity at each visit.
- Change from baseline in number of joints with active arthritis at each visit.

- Change from baseline in number of joints with limitation of motion at each visit.
- Change from baseline in index of inflammation (C-reactive protein [CRP] and Erythrocyte Sedimentation Rate [ESR]) at each visit.
- Childhood Health Assessment Questionnaire (CHAQ) at each visit:
  - Change from baseline in Parent's Assessment of Physical Function (CHAQ Disability Index).
  - Change from baseline in Parent's Assessment of Child's Arthritis Pain (CHAQ Discomfort Index, Visual Analog Scale [VAS]).
  - Change from baseline in Parent's Global Assessment of Overall Wellbeing (CHAQ subsection, Visual Analog Scale [VAS]).
- JIA American College of Rheumatology (ACR) response at each visit.
- Occurrence of JIA ACR disease flare at each visit after Month 3.
- JIA ACR Clinical Inactive Disease status at each visit, and clinical remission at each visit after 24 weeks since study start. Note that clinical remission is counted as 6 months (24 weeks) of inactive disease during study, and 24 weeks will be used in programming.
- Change from baseline in Juvenile Arthritis Disease Activity Score (JADAS) 27 CRP and JADAS-27 ESR, and occurrence of JADAS minimum disease activity and inactive disease at each visit.
- Achieving eligibility of tapering for corticosteroids, methotrexate (MTX)/leflunomide, and tofacitinib, respectively.
- Achieving partial tapering success for corticosteroids, MTX/leflunomide, and tofacitinib, respectively.
- Achieving complete tapering success for corticosteroids, MTX/leflunomide, and tofacitinib, respectively.
- In subjects with sJIA: achieving "Absence of Fever", defined as absence of fever due to sJIA in the week preceding the assessment at each visit.
- In subjects with Enthesitis Related Arthritis (ERA): Change from baseline in the Tender Enthesial Assessment (TEA), Modified Schober's Test, Overall Back Pain and Nocturnal Back Pain responses at various visits.
- In subjects with psoriatic arthritis (PsA): Change from baseline in body surface area (BSA) affected by psoriasis and Physician's Global Assessment (PGA) of psoriasis at various visits.

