### **The Clinical Inactive Disease:**

The Clinical Inactive Disease Status Determination assessment is a derived measurement and defined as follows: which includes:

- No joints with active arthritis.
- No fever, rash, serositis, splenomegaly, hepatomegaly, or generalized lymphadenopathy attributable to JIA.
- No active uveitis (as defined by the SUN Working Group).
- ESR or CRP levels within normal limits in the laboratory where tested or, if elevated, not attributable to JIA. There will be two endpoints: Clinical Inactive Disease Status defined by ESR and Clinical Inactive Disease Status defined by CRP.
- Physician global evaluation of disease activity score of ‘best possible’ on the scale used.
- Duration of morning stiffness of  $\leq 15$  minutes.

Since uveitis exam will be performed annually, for the purpose of determining JIA ACR Inactive Disease status, the last uveitis assessment result will be carried forward up to the next non-missing uveitis assessment prior to study discontinuation.

After the pre-processing of uveitis assessment, if any of the components is missing, the components that are not missing will be used to determine the Clinical Inactive Disease Status as follows:

- Inactive disease: all components must be present (non-missing) and meet all conditions.
- Active disease: at least one component is present (non-missing) and does not meet the condition.
- Not determined: any other scenarios.

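### Children who roll over on the day of their index-study final visit cannot reach clinical remission at an on-schedule Month 6 visit, because the 24-week count uses only in-study data and they have no in-study assessment at entry

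*SAP*

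**What the plan says.** Three rules in the SAP combine.

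- **What counts.** Appendix 1.5, under Clinical Remission on Medications: "Note that when calculating clinical remission, only inactive disease in this study will be included in the 24 weeks count". Section 3.2 agrees: "clinical remission is counted as 6 months (24 weeks) of inactive disease during study, and 24 weeks will be used in programming".
- **When it is reported.** Section 3.2 lists "clinical remission at each visit after 24 weeks since study start".
- **What makes a visit inactive.** Appendix 1.5 sets a completeness rule: "Inactive disease: all components must be present (non-missing) and meet all conditions". A visit with a missing component and no failed one is left undetermined.

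The protocol then decides who has data at entry. Section 6.1.2 covers same-day entry: "Subjects who complete their combined Screening/Baseline Visit on the same day as EOS in the qualifying/index tofacitinib study must also complete the following procedures". The list that follows contains consent, adverse events, the thromboembolism risk check, the contraception check and dispensing. In the Schedule of Activities, the column for entry combined with the index final visit is blank for physician global, joint assessment, morning stiffness, CRP and ESR. Section 7.1.5 confirms this for the two inflammatory markers, which are measured "at each study visit except Screening/Baseline Visit for subjects who roll over on the same day of EOS from their Index Studies". Children who enter on a separate day within 14 days (Section 6.1.3), or after 14 days (Section 6.1.1), do have these assessments at entry.

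The protocol's own definition of remission (Section 7.1.7) has no in-study restriction.

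**The concern.** Section 3.2 opens remission reporting just when a Day 1 assessment would complete 24 weeks. That timing works for children assessed at entry. It does not work for same-day rollovers, whose in-study record of disease activity starts a month later.

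The secondary objective is persistence of efficacy. SAP 6.2 and Table 2 call for remission to be summarised by visit in five analysis sets and plotted over time in three of them (sJIA1, sJIA2 and pJIA). If one standard entry route cannot contribute a remission at Month 6 but can at Month 9, the first point of the curve mixes routes that can qualify with one that cannot. Part of any rise from Month 6 to Month 9 then comes from the clock. In an uncontrolled study, a reader could take that rise for benefit still accruing on treatment.

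**Working it through.** **Inputs**

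- Required duration: 24 weeks, continuous (SAP 3.2, Appendix 1.5).
- On-schedule visits: target days from SAP Appendix 1.12, with the protocol's tolerance of ±5 days for Months 1 and 3 and ±10 days from Month 6. Month 1 = Day 25 to 35; Month 3 = Day 85 to 95; Month 6 = Day 170 to 190; Month 9 = Day 260 to 280.
- SAP label windows (Appendix 1.12): Month 1 = Days 2 to 60; Month 6 = Days 136 to 225.

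**Step 1: reproduce the plan's own timing.** 24 × 7 = 168 days. Counting from Day 1, 168 days are complete on Day 169. The first scheduled visit after that is Month 6, as Section 3.2 implies.

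**Step 2: children assessed on Day 1.** Span to Month 6 = visit day − 1.

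- Shortest: 170 − 1 = 169 days.
- Longest: 190 − 1 = 189 days.

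Both exceed 168, so remission is reachable at any on-schedule Month 6 visit.

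**Step 3: same-day rollovers, first in-study status at Month 1.** Span to Month 6 = Month 6 day − Month 1 day.

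| Case | Span | Against 168 |
|---|---|---|
| Longest | 190 − 25 = 165 | 3 days short |
| Nominal | 180 − 30 = 150 | 18 days short |
| Shortest | 170 − 35 = 135 | 33 days short |

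Counting both end days adds one day, so the maximum becomes 166, still short.

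**Step 4: first visit that works.** The shortest span from Month 1 to Month 9 is 260 − 35 = 225 days, which exceeds 168. Month 9 is the earliest on-schedule visit. If Month 1 is missed, Month 3 to Month 9 spans 260 − 95 = 165 to 280 − 85 = 195 days, which is usually but not always enough.

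**Step 5: how far the result depends on visits being on schedule.** With Month 1 on Day 25, 30 or 35, the 168 days are reached on Day 193, 198 or 203. Those days lie outside the protocol's Month 6 tolerance but inside the SAP's Month 6 label, which runs to Day 225. A late visit can therefore qualify.

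**Step 6: size.** Let p be the share of same-day rollovers among subjects at Month 6, and r the share of them who would qualify if Day 1 status were available. If they stay in the denominator as non-remitters and attend on schedule, Month 6 remission is low by p × r. If they leave the denominator, the Month 6 figure describes the other routes only. The documents give neither p nor r, and do not say which denominator applies.

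**The case against.** **Same-day final-visit data may already count as in-study.** The index final visit can be combined with this study's screening and baseline visits, and SAP 3.4.1 names such a combined visit as a possible source of extension baseline. But that section also limits extension baseline to data held in the extension database, and treats values not planned at entry as unavailable. It is written for baseline, and Appendix 1.5 does not say whether it extends to remission. So there is some ambiguity, but the only related rule points away from using those data.

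**The contrast between routes depends on the eye examination.** Inactive disease requires a uveitis result, and neither route within 14 days schedules an eye examination at entry. Both the Month 9 date and the contrast with separate-day entrants assume that the last index-study eye result is carried forward. This stands as a stated assumption.

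**The in-study rule is deliberate, and little depends on it.** It is stated twice, no hypothesis is tested, and inactive disease is reported separately at every visit. That limits the weight of the point. It does not make Month 6 comparable across entry routes.

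**Stronger readings that the documents do not support:**

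- *These children are scored as failures.* The SAP does not say so. Missing data are not imputed, incomplete status is undetermined, and no denominator for remission is given.
- *All index-study inactive time should count, since Protocol Appendix 4 counts "time in parent study and A3921145 inclusive".* That wording governs corticosteroid tapering only, and the SAP's tapering endpoints follow the investigator's decision rather than derived remission. A3921104 had a placebo withdrawal phase, and SAP 3.4.1 describes A3921165 as randomised withdrawal too. Full credit could therefore count time on placebo as persistence of tofacitinib effect.
- *Every other efficacy endpoint for these children runs from the index baseline.* Flare is measured from Month 3 of this study, and several endpoints are current status rather than change.
- *The shortfall is a known number.* Taking p as 50 to 80% and r as 20 to 30% gives 0.5 × 0.20 = 10 points to 0.8 × 0.30 = 24 points, but all of those inputs are assumptions.

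**Conclusion.** The point holds in a limited form. Under the rule as written, a same-day rollover cannot be in clinical remission at an on-schedule Month 6 visit: at most 165 days are available against 168. The earliest on-schedule visit is Month 9. Children assessed on Day 1 can qualify at Month 6.

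Only Month 6 is affected, and late visits within its SAP label can escape the restriction. Whichever denominator is used, the Month 6 figure mixes entry routes or omits one, and part of any rise to Month 9 is produced by the clock. The size cannot be computed from the documents.

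The conclusion rests on three assumptions: the 24 weeks run from the first in-study inactive assessment and not from study start; same-day index data are not treated as in-study; and index-study eye results are carried forward.

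**What to change.** In SAP Appendix 1.5 and Section 3.2, state that for same-day rollovers the index-study final-visit assessment serves as Day 1 inactive-disease status for the remission count, with the last index-study uveitis result carried forward. The span to an on-schedule Month 6 visit then becomes 169 to 189 days, the same as for children assessed on Day 1 under this protocol.

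Alternatively, keep the in-study rule and declare these children not evaluable for remission, and out of the denominator, before Month 9.

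In either case, do not credit index-study time before that final visit, because it may include placebo withdrawal.

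The cost is SAP wording and minor programming, plus use of one index-study visit under the first option. No new data are collected, and index-study values are already used for baseline.

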### **Appendix 1.6. Juvenile Arthritis Disease Activity (JADAS-27 CRP and JADAS-27 ESR) Score**

JADAS-27 CRP and JADAS-27 ESR score consists of four components (Consolaro 2009, Bazso 2009, Nordal 2012):

- Physician global assessment of disease activity;
- Parent/legal guardian/subject global assessment of Child well-being (from the CHAQ);
- Number of joints with active disease (27 joint assessment);
- CRP or ESR.

The 27 joints used here are bilateral Elbow, Wrist, MCP 1-3, PIP 1-5, Hip, Knee and Ankle, plus Cervical Spine.

The CRP value will be normalized to a 0 – 10 scale according to the following formula:

$$(\text{CRP (mg/L)} - 2.87)/10$$

Before calculation, CRP values <2.87 mg/L will be converted to 2.87 and CRP values >102.87 mg/L will be converted to 102.87. The value 2.87 (mg/L) here is the upper bound of the reference range provided by the lab.

The ESR value will be normalized to 0 – 10 scale as below:

$$(\text{ESR} - 20)/10$$

Before calculation, ESR values <20 mm/h will be converted to 20 and ESR values >120 mm/h will be converted to 120.

JADAS-27 CRP/ESR score will be calculated as the simple linear sum of the scores of its 4 components, which yields a global score of 0 – 57 for the JADAS-27 CRP/ESR score.

If any of the components is missing, the JADAS-27 CRP/ESR score will be considered missing.

### Appendix 1.7. JADAS-27 High Disease Activity, Moderate Disease Activity, Low Disease Activity, Minimal Disease Activity and Inactive Disease

The cutoff values in the JADAS-27 that correspond to inactive disease and minimal/low/moderate/high disease activity (Consolaro 2012, Consolaro 2014, Consolaro 2016) are defined as follows:

#### Polyarthrititis (>4 active joints) at baseline:

- Minimal Disease Activity:  $\leq 3.8$ .
  - Inactive Disease:  $\leq 1.0$ .
  - Low Disease Activity:  $> 1.0 - \leq 3.8$ .
- Moderate Disease Activity:  $> 3.8 - \leq 8.5$ .
- High Disease Activity:  $> 8.5$ .

#### Oligoarthritis ( $\leq 4$ active joints) at baseline:

- Minimal Disease Activity:  $\leq 2.0$ .
  - Inactive Disease:  $\leq 1.0$ .
  - Low Disease Activity:  $> 1.0 - \leq 2.0$ .
- Moderate Disease Activity:  $> 2.0 - \leq 4.2$ .
- High Disease Activity:  $> 4.2$ .

For JADAS-27 inactive disease and minimal/low/moderate/high disease activity for extended oligoarthritis, polyarthrititis RF+, polyarthrititis RF-, systemic JIA, PsA and ERA subjects with >4 active joints at baseline, the cutoff values of polyarthrititis will be used. For JADAS-27 inactive disease and minimal/low/moderate/high disease activity for PsA, ERA and systemic JIA subjects with  $\leq 4$  active joints at baseline, the cutoff values of oligoarthritis will be used.

Note that both JADAS-27 CRP and JADAS-27 ESR score will be used as cut-off values, so there will be two sets of JADAS minimum/low/moderate/high disease activity and inactive disease, one uses JADAS-27 CRP and the other uses JADAS-27 ESR.

### Appendix 1.8. Tapering of Corticosteroids, MTX/Leflunomide, and Tofacitinib

Data for tapering calculation will be captured in CRF. For each drug (Corticosteroids, MTX/Leflunomide, and Tofacitinib), if the subject start tapering based on investigator's judgment, the subject is considered eligible for tapering; if the subject's dose level goes down to a lower level by the end of study, the subject is considered achieving partial tapering

success; if the subject completely tapered off the drug, the subject is considered achieving complete tapering success.

- Proportion of subjects achieving eligibility of tapering = number of subjects who took the drug and started tapering/number of subjects who took the drug;
- Proportion of subjects achieving partial tapering = number of subjects who were able to undergo tapering from one dose level to a lower dose level/number of subjects who took the drug;
- Proportion of subjects achieving complete tapering = number and percentage of subjects discontinued drug completely/number of subjects who took the drug.

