2.2.2. Secondary

The following efficacy parameters will be assessed:

- Physician global evaluation of disease activity at each visit.
- Number of joints with active arthritis at each visit.
- Number of joints with limitation of motion at each visit.
- Index of inflammation (C-reactive protein [CRP] and Erythrocyte Sedimentation Rate [ESR]) at each visit.
- Childhood Health Assessment Questionnaire (CHAQ) at each visit.
 - Parent's Assessment of Physical Function (CHAQ Disability Index).
 - Parent's Assessment of Child's Arthritis Pain (CHAQ Discomfort Index, Visual Analog Scale [VAS]).
 - Parent's Global Assessment of Overall Wellbeing (CHAQ subsection, Visual Analog Scale [VAS]).
- JIA American College of Rheumatology (ACR) response at each visit and occurrence of JIA ACR disease flare after Month 3.
- JIA ACR Clinical Inactive Disease status and Clinical Remission on Medication at each visit.
- Change from baseline in Juvenile Arthritis Disease Activity Score (JADAS) 27- CRP and JADAS 27-ESR, and occurrence of JADAS minimum disease activity and inactive disease at each visit.
- Eligibility of tapering defined per protocol for corticosteroids, MTX/leflunomide, and tofacitinib.
- In subjects with **sJIA**: "Absence of Fever", defined as absence of fever due to sJIA in the week preceding the assessment at each visit.

- In subjects with Enthesitis Related Arthritis (**ERA**): Change from baseline in the Tender Enteseal Assessment, Modified Schober's Test, Overall Back Pain and Nocturnal Back Pain responses at various visits.
- In subjects with psoriatic arthritis (**PsA**): Change from baseline in body surface area (BSA) affected by psoriasis and Physician's Global Assessment (PGA) of psoriasis) at various visits.

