5.5.2.2. Permitted Dose Adjustments (Tapering) in Background JIA Therapies (Inactive Disease)

For subjects who experience improvement in JIA symptoms refer to [Appendix 4](#) for permitted tapering of background JIA therapies. See [Section 7.1.7](#) for definition of inactive disease.

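### SAP Appendix 1.8 reports tapers started under the name of protocol-defined eligibility, and its complete-success formula is looser than its own narrative

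*SAP*

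**What the plan says.** Protocol Section 2.2.2 lists as a secondary endpoint "Eligibility of tapering defined per protocol for corticosteroids, MTX/leflunomide, and tofacitinib". The definition it points to is in Appendix 4. Section 5.5.2.2 sends the reader there ("For subjects who experience improvement in JIA symptoms refer to" that appendix), and Appendix 4 opens with the rule "Subjects who have inactive disease for at least 24 consecutive weeks may begin to taper off of concomitant JIA therapies and tofacitinib". It then fixes the order: corticosteroids, MTX/leflunomide, tofacitinib. Where a drug is not in use the sequence shortens: "For subjects who are not taking concomitant oral corticosteroids, tapering will start with MTX/leflunomide, followed by tofacitinib". The corticosteroid condition is "inactive disease for at least 24 consecutive weeks (time in parent study and A3921145 inclusive", so inactive weeks in the parent study count for that drug. MTX/leflunomide needs a further 24 inactive weeks after the last corticosteroid dose. Tofacitinib needs a further 24 after the last MTX/leflunomide dose.

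SAP Section 3.2 lists eligibility without the reference to the protocol definition. It also adds two endpoints that the protocol does not have: partial and complete tapering success. SAP Appendix 1.8 begins "Data for tapering calculation will be captured in CRF" and then gives the working rule: "if the subject start tapering based on investigator's judgment, the subject is considered eligible for tapering". The eligibility numerator is subjects who took the drug and began a taper. The denominator for all three proportions is everyone who took the drug. For complete success, the narrative sentence requires the subject to have come off the drug by tapering, but the formula is "number and percentage of subjects discontinued drug completely/number of subjects who took the drug". SAP Table 2 reports all three tapering endpoints in all five efficacy analysis sets.

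**The concern.** Eligibility to taper and the decision to taper are different quantities. Appendix 4 is permissive: a child who meets it may be tapered but need not be. The protocol also allows background drugs to be reduced or stopped by other routes. Appendix 1 lets subjects reduce or stop a permitted DMARD with no disease condition. Appendix 3 allows adjustment for improvement from enrolment, and allows safety adjustments at any time. If a table headed eligibility counts tapers started, it leaves out children in sustained inactive disease whose treatment was kept unchanged. It may also take in children whose disease was not inactive.

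The complete-success formula raises a separate problem. It carries no condition on the reason for stopping, so on its wording a child who leaves because tofacitinib did not work is a tapering success. The clinical inactive disease and remission tables do not repair either problem, because they do not show which tapers met the criteria.

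**Working it through.** The plan gives no expected tapering rate, so there is no stated figure to reproduce. The check is a comparison of the two rules, with one piece of arithmetic for complete success.

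**1. Inactive time required.** SAP Appendix 1.8 checks none for any drug. Protocol Appendix 4 requires:
- Corticosteroids: 24 weeks, parent-study time included.
- MTX/leflunomide, no corticosteroids: 24 weeks.
- MTX/leflunomide, on both: 24 + T + 24 = 48 + T weeks, where T is the corticosteroid taper. Stepping down 1 mg/day each week from 5 mg/day takes 4 to 5 weeks, giving 52 to 53. T is longer from a higher dose, and could be 0 because Appendix 4 also permits discontinuation.
- Tofacitinib, on all three: 24 + T + 24 + U + 24 = 72 + T + U weeks, where U is the MTX/leflunomide taper (0 if stopped abruptly, which Appendix 4 accepts).

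**2. How the counts differ.** Among users of a drug, let A be those who meet Appendix 4, B those in A who are not tapered, and C those outside A whose dose is reduced or stopped and recorded as a taper. The protocol count is A. The SAP count is A − B + C, so the error is C − B and can have either sign. The documents give neither B nor C. Purely as an assumed illustration with 100 users and A = 40:
- B = 20, C = 0 gives 20.
- B = 10, C = 10 gives 40, of whom only 30 meet Appendix 4.
- B = 0, C = 30 gives 70, of whom 40 (57%) meet it.

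**3. What the CRF could change.** If the CRF accepts only Appendix 4 tapers, C = 0. B is unaffected, because the SAP numerator requires a taper to have started. The Appendix 1 route concerns DMARDs only, and the Appendix 3 routes concern background drugs. C is therefore mainly a matter for corticosteroids and MTX/leflunomide.

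**4. Complete success for tofacitinib.** Inputs are from the interim analysis in Protocol Section 2.3.2 (cutoff 4 June 2019): 227 enrolled, 2 of them not treated, 177 ongoing.
- Treated: 227 − 2 = 225.
- Not ongoing: 225 − 177 = 48, taking the 177 to be treated subjects.
- Share: 48/225 = 21.3%.

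This is a ceiling on withdrawals that fit the formula's wording. It is reached only if all 48 stopped other than by taper and the formula is applied literally. It is 0 if the CRF or programming limits the count to tapers. The same section names insufficient clinical response as the commonest reason for discontinuation. The formula also has no exclusion for drug stopped because participation ended.

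**The case against.** The strongest defence is that the CRF is not in the documents and may do the work. Protocol Section 7.1.7 bases inactive disease on the investigator's assessment, so investigator's judgment in the SAP could mean a judgment that Appendix 4 is met. That is a fair reading, and it could bring C and the counted withdrawals to 0. It does not rescue eligible children who were not tapered. The SAP also does not state it.

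Several stronger inferences are tempting and should not be drawn:
- A reader might infer that the SAP departs from the protocol on all three tapering endpoints. Only eligibility is a protocol endpoint. Partial and complete success exist only in the SAP, so the fault in complete success is internal inconsistency.
- A reader might infer that about a fifth of treated children would be reported as tapering successes. The narrative sentence and the label of the formula both point to tapering, and the 48 had left for any reason. The documents support a range from 0 to 21.3%, not an estimate.
- A reader might infer that the plan lets treatment be tapered without inactive disease. Appendix 1.8 is a reporting rule. Appendix 4 still governs when tofacitinib may be tapered, and the other permissions for background drugs may be intended.
- A reader might infer a breach of the commitment in Protocol Section 9 to amend the protocol for major changes to endpoint definitions. Whether this change is major is a judgment the documents do not settle, and SAP Section 2 ties that commitment to the primary endpoint.

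It also stands that the SAP states its rule openly and that no hypothesis is tested.

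**Conclusion.** The point holds in two parts. First, the row called eligibility measures tapers started, not the quantity that Protocol Section 2.2.2 names. The omission of eligible children who were not tapered follows from the SAP's wording alone. The inclusion of other reductions depends on what the CRF accepts. The net size and direction are unknown. Second, the complete-success formula contradicts the sentence before it and, read literally, admits treatment failures. Its reach for tofacitinib at the 2019 interim lies between 0 and 48/225 = 21.3%, and the upper end assumes that none of the 48 stopped by taper. For corticosteroids and MTX/leflunomide the documents give no frequency. The consequence is confined to descriptive secondary endpoints. No test, sample size or primary safety analysis is touched. It should still be corrected, because a label of eligibility or success should not depend on unstated programming.

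**What to change.** Change SAP Appendix 1.8 in three places.

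1. Relabel the current eligibility row as tapers started.

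2. Add an eligibility row for each of the three drugs, derived from Appendix 4 whether or not a taper began. Use the SAP Appendix 1.5 inactive-disease status (stating whether the ESR or the CRP version leads), actual visit dates and recorded dose dates. Keep everyone who took the drug as the denominator and split it into eligible, not eligible and not determined. State the tofacitinib wait for subjects on corticosteroids but not MTX/leflunomide, because Appendix 4 ties that wait to the last MTX/leflunomide dose.

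3. Count complete success only for subjects who started a taper and stopped the drug through it. Exclude withdrawals and end-of-participation stops. Say how a later restart, which Appendix 4 allows, is treated.

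The cost is one text change, one derivation per drug and a few table rows. Visit-level inactive disease and a 24-week run are already derived for clinical remission, and Protocol Section 5.5 requires doses and dates to be recorded. Twenty-four weeks is 168 days. Three consecutive 3-monthly visits span 180 days, or 160 to 200 with ±10-day windows, so three inactive visits usually suffice and spans of 160 to 167 days need a fourth.

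There are limits to state:
- The remission run counts only time in this study, so the corticosteroid clock needs linked parent-study status. For the 26 subjects of A3921103, dosed for 5 days, this adds little.
- Appendix 1.5 needs every component present, and Protocol Section 7.2.5 does not require a uveitis exam in sJIA. sJIA subjects without a uveitis record will often fall under not determined and should be visible there.
- SAP Appendix 1.2 scores injected joints as affected from the injection onward, so those subjects cannot be classed inactive.
- Section 5.5 asks for the indication, not the reason for a dose change, so safety stops may not separate from stops for improvement.

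With the denominator unchanged, complete success can only fall or stay the same. Eligibility can move either way.
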